10.4.3 ANALYSIS OF THE SECONDARY ENDPOINT(S)

See above.

10.4.4 SAFETY ANALYSES

All adverse events will be measured daily and recorded at the end of each condition for each subject, calculated dichotomously based on its emergence during the treatment timeframe. These outcomes will be presented in tables for review by the DSMB, and such outcomes will be accompanied by descriptive and inferential statistics (both mean

CLEAR 2 Study Protocol: Hormones and Suicide Risk, Version 9, 07-02-2020, Page 43 of 64

levels and change from baseline in each condition) to determine whether AEs and changes in AEs are more likely to occur in the experimental conditions.

Below, we list the adverse events that are most likely to occur in the course of the study and will therefore be monitored most closely (at every daily and weekly participant contact during administration of study agents). However, participants will have the opportunity to report any other adverse event in addition to those listed below.

GENERAL ADVERSE EVENTS

- Significant deterioration in mood
- Significant deterioration in suicidality
- Any adverse event related to venipuncture
- Any adverse event related to emotional or behavioral reactions to interviews, questionnaires, or tasks

ESTRADIOL PHYSICAL SIDE EFFECT ADVERSE EVENTS

The most frequent side effects associated with estradiol use include:

- breast tenderness (occurs in 29% of patients)
- abdominal cramps (occurs in 16% of patients)
- headache (occurs in 13% of patients)
- edema (swelling) (occurs in 10% of patients)
- nausea (occurs in 6% of patients)
- acne (occurs in 3 12% of patients)

- skin rash or irritation may also occur at site where the patch is placed (occurs in 3 - 12% of patients)

Rare side effects (<1%) include:

- jaundice (yellowing of skin)
- increased blood pressure
- worsening of migraines or asthma
- enlargement of uterine fibroids
- intolerance to contact lenses
- dizziness
- changes in appetite and weight

PROGESTERONE PHYSICAL SIDE EFFECT ADVERSE EVENTS

The most common side effects associated with progesterone include:

- breast tenderness (occurs in 16% of patients)
- dizziness (occurs in 24% of patients)
- abdominal cramping (occurs in 20% of patients)
- headache (occurs in 16% of patients)
- viral infection (occurs in 12% of patients)
- joint pain (occurs in 12% of patients)
- diarrhea (occurs in 8% of patients)

- menstrual bleeding, sometimes consistent with a heavy menstrual period (occurs in 20-30% of

patients) - drowsiness (occurs in 9% of patients)

Rare (<1%) side effects include:

- vaginal discharge
- chest pain
- abdominal bloating

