Safety and Feasibility Information. In a recently-completed similar experimental study by the PI (the K99-funded study), no serious adverse events have been recorded. Just two participants were withdrawn (by the study team; 0 dropouts) after randomization, supporting protocol feasibility. Missing data were minimal; participants completed 90% of daily symptom surveys, 97% of blood draws, and 100% of lab visits.

Results from Previous Experiment (Fig 2, above): E2/P4 withdrawal causes perimenstrual worsening of daily self-reported suicidality in at-risk females, and EXPERIMENTAL STABILIZATION REDUCES THIS

RISK. Analyses of daily self-report data from the previous study (n = 30) indicates that perimenstrual hormone stabilization in the active condition *prevented* the robust perimenstrual increase in suicidal ideation observed under placebo (E2/P4 natural withdrawal). Results are identical for suicidal planning, suggesting the applicability of these results to suicidal behavior as well as suicidal thoughts. Further, as predicted, perimenstrual risk was *shifted* to the "withdrawal week" of the active condition (not significantly different from natural perimenstrual levels of risk under placeboi.e., the risk is not higher, but simply experimentally shifted to 2 weeks later), further demonstrating the causal role of ovarian steroid withdrawal in perimenstrual worsening of suicidality. When results were standardized to reflect subject-specific means and standard deviations (as in Fig 2 at right), the average impact of stabilization was roughly a 1 personstandard-deviation condition difference in suicide outcomes. This suggests clinical significance.

Fig 2: Preceding Study - Experimental Effects on Suicidality

Additional analyses using task and interview data are planned to identify the specific cognitive and behavioral constructs that account for experimental effects on suicidality outcomes.

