6.1.9 DURATION OF THERAPY

The planned duration of active treatment is 14 days. All days in which participants use patches and pills will be utilized in multilevel modeling analyses, which accommodate unbalanced/missing data.

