7.3.3 FOLLOW-UP

Following the baseline/enrollment visit, participants will remain in contact with study staff and will begin ovulation testing as instructed. When ovulation testing is positive (day 0), the participant will contact the study staff to schedule the first three laboratory assessment visits (visits for condition 1) on days +7, +14, and +22. All laboratory assessment visits are identical in structure and content, with the singular exception that the first laboratory visit of each condition will include: (1) a pregnancy test that must be negative prior to dispensing study medication, (2) a urine drug screen, and (3) assessment of height and weight (BMI). Between conditions, participants will again remain in contact with study staff to schedule ovulation testing in the next menstrual cycle. Once again, when ovulation is confirmed (day 0), the final 3 laboratory assessments (for condition 2) will be scheduled on days +7, +14, and +22. These visits may be scheduled up to +/-2 days in either direction.

Variable	Interview Measure	Self-Report Measure	Task Measure					
Vitals (first lab of each condition)	-	-	Height/Weight					
Urine Pregnancy Screen (first lab of each condition)	-	-	x					
Urine Drug Screen (first lab of each condition)	x	Х	x					
Blood Sample (48 ml)	-	-	E2/P4/ALLO/Inflammatory Gene Expression					
Suicidality	Full SITBI	-	-					
Depression	-	CESD	-					
Hopelessness	-	BHI	FT-IRAP					
Inhibitory Control	-	UPPS-P	SST					
Threat Sensitivity	-	STAI	DPT					
Negative Social Appraisals	-	SSES	SAR-IAT					
Side Effects, AEs, and Compliance Monitoring	Х	-	-					
Parasympathetic Activity	-	-	Respiratory Sinus Arrhythmia					

• Follow-Up Assessments Administered (see section 4.1 for Abbreviations):

Follow-Up Timeline:

Condition 1 (Follow-Up Visits 1-3):

- Ovulation Testing

- Positive Ovulation Test #1= Day 0

- Study Followup Visits 1-3 Scheduled for days +7, +14, +22

- Study Followup Visit 1 (Day +7): Assessments, pregnancy test, drug test, vitals, administration of study agent patch A and dispensation of pills (Condition 1)

- Study Followup Visit 2 (Day +14): Assessments, replacement of study agent patch A with patch B (Condition 1)

- Removal of study patch and end of pills on day +21

- Study Followup Visit 3 (Day +22): Assessments

CLEAR 2 Study Protocol: Hormones and Suicide Risk, Version 9, 07-02-2020, Page 33 of 64

Condition 2 (Follow-Up Visits 4-6):

- Ovulation Testing
- Positive Ovulation Test #2= Day 0

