8.3 TIME PERIOD AND FREQUENCY FOR EVENT ASSESSMENT AND FOLLOW-UP

The occurrence of an AE or SAE may come to the attention of study personnel during study visits and interviews of a study participant. All AEs including local and systemic reactions not meeting the criteria for SAEs will be captured on the appropriate documentation. Information to be collected includes event description, time of onset, clinician's assessment of severity, relationship to study product (assessed only by those with the training and authority to make a diagnosis), and time of resolution/stabilization of the event. All AEs occurring while on study must be documented appropriately regardless of relationship. All AEs will be followed to adequate resolution.

Pre-existing medical conditions are exclusionary for participation in the trial, with the exception of psychiatric conditions. Any psychiatric condition or symptom that is present at the time that the participant is screened, including mood symptoms and suicidal *ideation*, will be considered as baseline and not reported as an AE. However, if the study participant's condition or symptom deteriorates significantly with regard to the severity or impact of the symptom on the participants functioning or safety (as determined by Drs. [name] and [name]) at any time during the study, it will be recorded as an AE. UPs will be recorded in the data collection system throughout the study.

Changes in the severity of an AE will be documented to allow an assessment of the duration of the event at each level of severity to be performed. AEs characterized as intermittent require documentation of onset and duration of each episode.

The PI will record all reportable events with start dates occurring any time after informed consent is obtained until 7 (for non-serious AEs) or 30 days (for SAEs) after the last day of study participation. At each phone call and study visit, study staff will inquire about the occurrence of AE/SAEs since the last visit. All AEs will be immediately reported to the PI, who will respond (psychiatric AEs) or consult with [name] as soon as possible (for medical AEs). Events will be followed for outcome information until resolution or stabilization.

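### The adverse-event tables count by an undefined treatment timeframe which, on its plain reading, includes withdrawal under placebo but largely misses the postponed withdrawal after progesterone stabilization (mainly Condition C)

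*Combined protocol and SAP*

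**What the plan says.** Section 10.4.4 measures AEs daily, records them at the end of each condition, and reduces each to yes or no, "calculated dichotomously based on its emergence during the treatment timeframe". Descriptive and inferential statistics go to the DSMB "to determine whether AEs and changes in AEs are more likely to occur in the experimental conditions". The listed general AEs include significant deterioration in mood and "Significant deterioration in suicidality". Close monitoring takes place "at every daily and weekly participant contact during administration of study agents".

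The treatment timeframe is not defined. The nearest statements are:
- Section 6.1.9: "The planned duration of active treatment is 14 days".
- Section 7.3.3: agent starts at the day +7 visit, then "Removal of study patch and end of pills on day +21".
- Section 10.4.1: each study period is days +7 to +22.

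On when withdrawal happens:
- Section 2.2: the dosing days cover the time of natural perimenstrual withdrawal.
- Section 2.1, on the preceding study: under active hormone "the risk is not higher, but simply experimentally shifted to 2 weeks later", with a size not significantly different from placebo.
- Section 2.3.1: stabilization merely delays normal withdrawal and adds no net risk.
- Section 4.1 (Participant Safety): risk is shifted during P4 stabilization.
- Section 4.1 (Primary Windows): tapered withdrawal from exogenous P4 in Condition C is placed at about +16 to +22.

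AE collection is wider than the counting rule. Section 8.3 states: "All AEs occurring while on study must be documented appropriately regardless of relationship". Phone measures run to five days after the last patch or pill (section 4.1).

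**The concern.** The manipulation is meant to move the time at which mood and suicidality worsen. A yes/no count in a window tied to agent days treats a shift in time as a fall in frequency. Deterioration on day +14 under placebo scores yes; the same deterioration on day +25 after P4 stabilization scores no, although a daily call still takes place on that day.

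The safety argument in section 2.3.1 is that risk is delayed and not increased. Testing it needs both the withdrawal that was prevented and the withdrawal that was postponed. A table with only the first can show an apparent benefit of Condition C and can hide an excess after removal. These are suicidality events in participants recruited for suicidal ideation.

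**Working it through.** The plan states no figure for this point, so there is nothing to reproduce. The check has two parts.

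**1. Overlap in days.** Natural withdrawal under placebo lies inside +7 to +21 (section 2.2), so every candidate window contains it. For postponed withdrawal I take the section 2.1 timing as +22 to +28, the week after the last agent. That is my assumption, since section 2.1 gives no day numbers. The alternative is +16 to +22 (section 4.1).

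| AE window | Days of +22 to +28 covered | Days of +16 to +22 covered |
|---|---|---|
| +7 to +21 (agent days) | 0 of 7 | 6 of 7 |
| +7 to +22 (study period) | 1 of 7 | 7 of 7 |
| +7 to +26 (last call: 21 + 5) | 5 of 7 | 7 of 7 |
| +7 to +28 | 7 of 7 | 7 of 7 |

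The result depends on which section gives the right timing and on what the timeframe means.

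**2. Illustrative size.** Let b be the ordinary weekly risk of a mood or suicidality AE and w the risk in a withdrawal week, with w equal in both conditions. Treat the agent days as two weeks. Both risks are assumed.

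Section 2.1 timing, agent-day window:
- Placebo (one withdrawal and one ordinary week): 1 − (1 − w)(1 − b)
- Condition C, if all withdrawal risk is postponed (two ordinary weeks): 1 − (1 − b)²

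With b = 5%, Condition C is 1 − 0.95² = 9.75%:

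| w | Placebo | Condition C | Spurious gap (points) | Events expected in 40 |
|---|---|---|---|---|
| 10% | 1 − 0.90 × 0.95 = 14.5% | 9.75% | 4.75 | 5.8 vs 3.9 |
| 20% | 1 − 0.80 × 0.95 = 24.0% | 9.75% | 14.25 | 9.6 vs 3.9 |
| 30% | 1 − 0.70 × 0.95 = 33.5% | 9.75% | 23.75 | 13.4 vs 3.9 |

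With b = 2%, Condition C is 1 − 0.98² = 3.96%, and the gaps are 7.8, 17.6 and 27.4 points.

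Counting the week after agent gives 1 − (1 − w)(1 − b)² in both conditions. At b = 5% that is 18.8%, 27.8% and 36.8%, and the gap is zero.

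Section 4.1 timing (+16 to +22), same agent-day window: six of the seven withdrawal days are counted. With risk spread evenly over the week, Condition C becomes 1 − (1 − w)^(6/7) × (1 − b)^(8/7). At b = 5% that is 13.8%, 22.1% and 30.5%, so the gaps fall to about 0.7, 1.9 and 3.0 points. With a window to +22 they vanish.

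**The case against.** A reader might infer that active hormone in general is made to look safer, by construction. The documents do not support that, for four reasons.

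- **The exclusion is an inference.** The timeframe is undefined, and recording at the end of each condition does not mean that later events are dropped. This stands. Still, the agent-day reading is the natural one. It matches the 14-day treatment in section 6.1.9, the monitoring wording in section 10.4.4 and the relatedness wording in section 8.5. The only other defined period ends one day later, and no section brings post-agent events into the condition tables.
- **Section 4.1 puts P4 withdrawal mostly on agent.** This stands as a conflict with section 2.1. It does not settle the matter: doses are fixed (section 6.1.7) and pills run to +21, so withdrawal from exogenous P4 cannot be complete before then. Section 7.3.4 adds a final visit because of risk after exogenous hormone stops.
- **Each active condition stabilizes one hormone only.** Condition B leaves natural P4 withdrawal inside the window, and section 4.1 predicts heightened suicidality in both A and B. Under that hypothesis the artefact between A and B is small. Condition C keeps estradiol withdrawal in its window, so the gaps above are too large to the extent that estradiol contributes. This stands.
- **Most AEs listed in section 10.4.4 are drug side effects.** Breast tenderness, dizziness and patch-site irritation arise while agent is taken, and an on-agent count does not understate them. This stands.

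A reader might also infer that late events are lost or that the DSMB could not see them. That is not supported either. They are still recorded (section 8.3), the DSMB specifies its own tables and reviews all serious AEs (section 8), and there is a final risk assessment (section 7.3.4). The gap is in the tabulation, not in safety capture.

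**Conclusion.** The point holds in a limited form. On the plain reading of section 10.4.4 and the section 2.1 timing, the between-condition comparison of mood and suicidality deterioration favours Condition C and cannot test the claim of delay without net increase. Condition B is affected much less.

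The direction rests on two things that the documents leave open: what the treatment timeframe means, and whether postponed withdrawal falls after +21 or at +16 to +22. The size is illustrative only, about 5, 14 or 24 points under the assumed 5% ordinary and 10%, 20% or 30% withdrawal-week risks. It further assumes that all of placebo's withdrawal risk is postponed in Condition C. On the +16 to +22 timing it is about 3 points or less. The point deserves correction before any comparative AE table is produced, because the repair is cheap and the events concerned are the most important ones in this population.

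**What to change.** In section 10.4.4:
1. Replace the undefined timeframe with one fixed window, identical for all three conditions, from first agent (+7) to a stated day after removal. Day +28 covers the whole of +22 to +28. Day +26, when daily calls end, covers 5 of 7 days; at b = 5%, with risk spread evenly over the week, it would leave about 1.3, 3.7 or 5.8 points of the illustrative gap.
2. Tabulate on-agent, post-agent and combined counts for each condition.
3. Base the comparison of mood and suicidality AEs on the combined count. On-agent counts remain suitable for drug side effects.
4. Reconcile the withdrawal timing in sections 2.1 and 4.1.

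Do not run the window to the start of the next condition. That would span a washout cycle with another natural withdrawal and give unequal follow-up after the last condition.

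The cost is mainly wording and table programming, since section 8.3 already requires these AEs to be documented. There are two drawbacks: slightly more background events in every condition, and sparser ascertainment after about +26.

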10.4.5 ADHERENCE AND RETENTION ANALYSES

Adherence to hormone administration protocols will be characterized following the close of the study using serum assays for E2 and P4 during the active conditions relative to hormonal profiles during the placebo condition; it will not be monitored in real time.

Participants will be monitored in their compliance daily during each study condition via a phone call with study staff. Any deterioration in adherence will be immediately remedied via increased reminders and phone calls.

10.4.6 BASELINE DESCRIPTIVE STATISTICS

Groups (counterbalanced orders) will be compared on demographic factors such as age, severity of perimenstrual mood change in the placebo condition, and general suicidality. However, inferential statistics are not necessary as our primary outcome modeling procedures will control for any baseline differences that exist.

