(Condition B) or P4 (Condition C) will be maintained for 14 days by applying a new patch on day +14 (extended luteal phase levels spanning +7 to +21), preventing natural withdrawal and stabilizing E2 or P4 in physiologic¹⁰² luteal range. In the prior study, this dosing schedule resulted in a stabilized, slower hormone taper as both endogenous hormones were naturally falling during the perimenstrual experimental time period, with exogenous hormone slowing/buffering this decline during the active phase. Of note, the placebo condition uses the same patch/pill schedule.

Assessment of Outcomes. In addition to daily surveys, participants will complete phone measures starting at ovulation and ending 5 days following the last patch/pill. Three lab sessions will assess serum E2, P4, and ALLO, and behavioral outcomes.

Lab Construct Measures. Each computerized task is scored using within-task comparisons, controlling for training-related changes in response time. **Hopelessness** will be measured via the Future Thinking Implicit Relational Assessment Procedure (FT-IRAP)¹⁰³; participants respond with *true* or *false* to pairings between "I expect" and "I don't expect" with sets of negative (e.g., worry, sadness) and positive (e.g., enjoyment, happiness) events. Greater latency to optimistic/hopeful, and lower latency to pessimistic/hopeless pairings indicate implicit hopelessness¹⁰³. Performance predicts clinical hopelessness and depression¹⁰³. Negative **Social Appraisals** will be measured using the Social Acceptance-Rejection Implicit Association Test (SAR-IAT)¹⁰⁴, in which participants respond to pairings of *self* words (e.g., I, me) and *other* words (e.g., them, you) with words indicate the strength of implicit self-with-acceptance or self-with-rejection associations. Performance predicts explicit social

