10.4 DESCRIPTION OF STATISTICAL METHODS

10.4.1 GENERAL APPROACH

The design of this study is a three-period crossover design, where each of three study periods is a perimenstrual frame of the menstrual cycle (days +7 to +22 following ovulation where positive ovulation test day=0). Each participant will complete all three conditions in a randomized order.

Primary hypothesis tests will be evaluated using a alpha level of .05, with a two-tailed test.

All outcomes will be checked for normality; given the low likelihood that suicidality will follow a normal distribution even in this clinical sample, we expect that we will need to utilize nonparametric procedures.

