10.4.2 ANALYSIS OF THE PRIMARY EFFICACY ENDPOINT(S)

Primary and secondary endpoints are operationalized above (i.e., mean within-person differences between conditions) for the daily SITB suicidal ideation and planning subscales (primary endpoints) as well as the daily UPPS-P impulsivity, PROMIS anxiety, CESD depression, BHI hopelessness, and SSES rejection sensitivity subscales (secondary endpoints).

Analyses will proceed identically for all outcomes listed above. First, we will calculate each subject's mean daily rating (via phone) on the outcome measure *during* each condition.

Second, we will utilize repeated measures ANCOVA to examine the within-person condition effects. Covariates (medicines, BMI, age) will be examined and included. These analyses will be conducted on the intent-to-treat dataset.

If necessary due to violations of model assumptions, we will utilize similar nonparametric tests.

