10.6 MEASURES TO MINIMIZE BIAS

10.6.1 ENROLLMENT/ RANDOMIZATION/ MASKING PROCEDURES

Individuals will be enrolled following phone screen and an enrollment visit as described above. Individuals will be randomized by IDS to one of six condition orders (permutations of A-B-C) following enrollment visit if they meet study criteria and give informed consent. Masking and blinding will be handled by IDS according to standard procedures for double blinding, and will be

CLEAR 2 Study Protocol: Hormones and Suicide Risk, Version 9, 07-02-2020, Page 46 of 64

fully double-blind. Randomization codes will be kept by IDS until the completion of the study, and will be shared only as needed for unblinding as needed for safety monitoring (described above).

Blinding and Compliance: Pills are dispensed in a double-blind manner. Patches will be placed by CTSA staff at UIC. All study staff will remain blinded. Preliminary analyses from the preceding similar experiment revealed that the blinding was successful; participants were not more likely to report believing they were on active treatment in the active condition relative to the placebo condition (p = .58). Participants will: **1**) be educated on the importance of compliance; **2**) be asked about compliance on each daily call; and **3**) have steroid levels measured to confirm compliance.

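### The primary model omits each condition's pre-dose suicidality score, so cycle-to-cycle variation stays as noise in the condition contrasts; the cost is precision, not bias

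*Combined protocol and SAP*

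**What the plan says.** Section 10.4.6 plans to compare the counterbalanced orders on age and on "severity of perimenstrual mood change in the placebo condition, and general suicidality". It then waives inferential tests because "our primary outcome modeling procedures will control for any baseline differences that exist".

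Section 10.4.2 gives the primary model: a repeated measures ANCOVA on each woman's mean daily phone rating during each condition. On adjustment it says: "Covariates (medicines, BMI, age) will be examined and included". The endpoint in 4.2.1 is a difference between conditions with no baseline subtracted. The multilevel alternative in 4.1 names no baseline covariate either.

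Section 10.2, by contrast, states the prediction for the primary endpoints as the change from Lab 1 to Lab 2 within each condition.

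On timing, 10.6.1 says: "Individuals will be randomized by IDS to one of six condition orders (permutations of A-B-C) following enrollment visit". Section 10.4.1 adds: "Each participant will complete all three conditions in a randomized order". It also defines each study period as days +7 to +22. For scores before dosing, 4.1 says "participants will complete phone measures starting at ovulation and ending 5 days following the last patch/pill", and 7.3.3 lists "Study Followup Visit 1 (Day +7): Assessments, pregnancy test, drug test, vitals, administration of study agent patch A", with a full SITBI among the assessments at each lab visit. A later sentence in 4.1 ties the daily suicidality call to active condition days.

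**The concern.** A participant is followed for roughly six to seven months. Her suicidality just before dosing can differ from cycle to cycle because of stressors or a mood episode. Those differences are not stable traits, so comparing a woman with herself does not remove them. They pass into every condition contrast as noise unless the model uses the pre-dose score from the same cycle. The 10.4.6 sentence suggests that this has been dealt with, but 10.4.2 contains nothing that does it.

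There is a separate labelling error. "severity of perimenstrual mood change in the placebo condition" is a response under one of the three compared conditions, seen in period 1, 2 or 3 depending on the order drawn. It cannot describe the groups before treatment.

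**Working it through.** **1. What the sentence covers.**

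| Source of difference | Handled by the 10.4.2 model? |
|---|---|
| Age, BMI, medicines | Yes, named as covariates |
| Stable level of suicidality, between women or orders | Yes, cancels in the within-person contrast |
| Pre-dose level that differs between a woman's own cycles | No |

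The second row was checked by simulation: six orders, three periods, 42 women, 400 replicates per setting, period terms included, true A–C difference 0.50. Raising the baseline of three of the six orders by 0, 1 or 3 units left the unadjusted mean estimate between 0.48 and 0.52. Stable imbalance does no harm.

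For the third row, with an assumed within-woman correlation of 0.6 between pre-dose and endpoint scores, the SD of the estimate was 0.145 to 0.162 without the period baseline and 0.123 to 0.130 with it. The mean stayed near 0.50 both ways. The omission costs precision and causes no bias.

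**2. The plan's own power figure.** Section 10.5 gives 80% power at f = 0.25 with 24 participants and states no correlation between repeated measures. Use noncentral F with λ = f²·N·m/(1 − ρ), m = 3 conditions, and (m − 1) and (N − 1)(m − 1) degrees of freedom. At an assumed ρ = 0.5, λ = 0.0625 × 24 × 3 / 0.5 = 9.0 and power is 74.1%; 80% needs N = 28. N = 24 is reached at ρ of about 0.57. Because ρ is unstated, the figure can be neither confirmed nor called wrong, and this point does not rest on it.

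**3. Gain from the covariate.** Let r be the within-woman correlation between a cycle's pre-dose score and its endpoint (not in the documents; a range is shown). The adjusted contrast variance is (1 − r²) times the unadjusted one. For a paired t test with n = 40 and two-sided alpha 0.05, a standardised difference of 0.454 gives 80% power. After adjustment it becomes 0.454/√(1 − r²), and the equivalent unadjusted sample is 40/(1 − r²).

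| r | Variance reduction r² | 40 act like | Power from 80% |
|---|---|---|---|
| 0.2 | 4% | 42 | 82% |
| 0.3 | 9% | 44 | 84% |
| 0.5 | 25% | 53 | 90% |
| 0.7 | 49% | 78 | 98% |

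The 80% start is a reference point. At f = 0.25, ρ = 0.5 and N = 40, λ = 0.0625 × 40 × 3 / 0.5 = 15 and power is already 93.5%. Adjustment then gives 95.5% at r = 0.3 and 98.2% at r = 0.5.

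**4. Covariate or change score.** A plain change score multiplies the contrast variance by 2(1 − r): 1.6, 1.4, 1.0 and 0.6 at r = 0.2, 0.3, 0.5 and 0.7. Below r = 0.5 it is worse than no adjustment, whereas the covariate never increases this variance apart from the degree of freedom it uses.

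**5. Are the scores pre-dose?** Section 7.3.2 says no agent is given before Lab 1, and 7.3.3 lists the assessments ahead of the patch and pills. That order is a listing, not a stated rule. Lab 1 may fall two days either side of day +7 (7.1.1, 7.3.3). A visit on day +5 would make the day +6 call post-dose, so a fixed window of days 0 to +6 is unsafe.

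**The case against.** The strongest reply is that 10.4.6 is about differences between counterbalanced orders, and for those it is largely right: each woman is her own control, and no inferential baseline test is needed. That stands. A reader might infer that the sentence is simply false, or that the model has no baseline at all. The documents do not support either reading: age, BMI and medicines are in the model, age is one of the factors 10.4.6 lists, and stable differences cancel by design.

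A reader might also infer that the pre-dose scores go unused throughout. They do not, because 10.2 builds its prediction on Lab 1. What can be said is that 4.2.1 and 10.4.2 do not carry that reference through.

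A third tempting reading is that the analysis conditions on a treatment response. Placebo-condition mood change is not among the 10.4.2 covariates; 10.4.6 only compares orders on it. The fault is one of labelling, and it would distort the analysis only if the sentence about control were applied literally to that variable.

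The remaining objections limit the size. The documents do not support any value of r, and at r = 0.2 the gain is under two percentage points of power. Sections 10.4.1 and 10.4.2 foresee nonparametric tests, to which the r² rule does not carry over directly. It is also unsettled whether the suicidality calls begin before dosing, and the Lab 1 full SITBI is not identical to the shortened version used in the calls.

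**Conclusion.** The point holds as a matter of precision. The specified model leaves out the pre-dose outcome score, so cycle-to-cycle variation in suicidality remains in the condition contrasts. Under randomised order this does not bias them. Contrast variance could fall by about r²: 4% to 49% for r from 0.2 to 0.7, or 80% power at 40 completers rising to between 82% and 98%. The gain is smaller if power is already higher or a nonparametric test is used. These figures rest on an assumed r, on complete data from 40 women, and on scores that are truly pre-dose. Separately, the placebo-condition variable is wrongly listed as baseline, and the promise to control for any baseline difference is wider than the model delivers.

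**What to change.** - **10.4.2:** add, for each woman and condition, the pre-dose score of the same outcome. Define it as all daily calls before that condition's actual first patch or pill, not as fixed days. If calls start only with drug, use the Lab 1 SITBI completed before dosing, and state that order as a rule. Enter the score as the deviation from her mean over the conditions she has, with that mean also in the model, so that non-completers have a defined value. Use ANCOVA, not a plain change score.
- **4.1:** reconcile the two sentences on when the calls start.
- **10.2, 4.2.1 and 10.4.2:** state consistently whether the primary comparison refers to the pre-dose score.
- **10.4.6:** remove placebo-condition mood change from the baseline factors, use the enrollment SITBI for general suicidality, and limit the sentence about control to what the model does.

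The cost is one or two degrees of freedom and a few wording edits, with no new data if the scores are collected as 4.1 and 7.3.3 describe. One downside should be stated in the plan: any residue of an earlier condition in the pre-dose days of periods 2 and 3 would be partly adjusted away.
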